4.1.11 Pulmonary Function Tests and Spirometry

Full pulmonary function testing is required at Cycle 1 Day 1. Only spirometry is required at day 1 of cycles 4, 7, 10, and 13, and EOT. Spirometry is required at day 1 of cycles 16, 19, and 22 if a patient has bronchiolitis obliterans syndrome or as clinically indicated.

4.1.12 Patient-Reported Outcomes

Subjects will complete the Lee Chronic GVHD Symptom Scale and the Patient-reported Outcomes Measurement Information System (PROMIS)-29 survey (See Appendix 10) at Day 1 of cycles 1, 4, 7, 10, 13, 16, 19, 22 and End of Treatment.

The Lee Chronic GVHD symptom scale (LSS) is a 30 item measure with one summary score and 7 domains: skin, mouth, eye, lung, psychoemotional, vitality and nutrition.^{40,41} Higher scores indicate higher symptom burden. Scores may be calculated if more than half of items in a subscale are answered. Scores range from 0-100 with higher scores indicated greater symptom burden. A difference of 6-7 points on the summary score is considered clinically meaningful but since this scale measures cGVHD symptoms, general population norms are not available.

The PROMIS-29 contains 29 scored items and 7 subscales: for the physical and social functioning scales, higher scores indicate better functioning; for fatigue, pain, anxiety, depression, and sleep scales, higher scores indicate a higher symptom burden.⁴² Similar to the SF-36, scores are normalized to 50 with a STD of 10 with higher scores indicating better functioning, and scores greater than 0.5 times STD (i.e., <45 or >55, compared to the general population) are considered clinically meaningful.

4.1.13 Clinician-Reported Outcomes

The NIH Chronic GVHD Response Assessment (Appendix 6) will be completed monthly, based on physical exam findings, testing and patient interviews. The assessment must be completed by a clinician.

4.1.14 Biologic Studies

These studies aim to discern the biologic impact of Hedgehog pathway inhibition in the treatment of cGVHD. Peripheral blood samples (20 mL in a heparinized tube and 4 mL in an EDTA tube) will be obtained on day 1 of cycles 1, 2, 4, and 7 and processed into peripheral blood mononuclear cells and plasma. Samples will be frozen and batch shipped to Fred Hutch for storage and potential study later depending on the clinical results of the trial. Four-millimeter punch biopsies will be obtained before and after 6 months of treatment with glasdegib in consenting patients. Patients may still participate in the trial if they refuse the research skin biopsies. Biopsies are bisected, with half stored in RNAlater, and half embedded in OCT (optimal cutting temperature compound), for later analysis. Skin biopsies will not be performed if there are contraindications as outlined in Manual of Operations.

4.1.15 Study Drug Accountability

Subjects will return unused medication at each study visit.

4.2 ASSESSMENT OF RESPONSE TO TREATMENT

Response assessments will be evaluated based on NIH Criteria (refer to Appendix 7).

4.3 END OF TREATMENT VISIT AND SAFETY FOLLOW-UP

An End of Treatment (EOT) visit is required for safety assessments for any subjects who permanently discontinue study drug for any reason, including after completing 24 months of treatment on study. The EOT visit should be scheduled within 28 days (with +/- 7-day window) after the last dose of study drug but is not required for subjects who discontinue from the study within 10 days of a completed, scheduled study visit.

If a patient is not willing or able to return for evaluation or is seen prior to 28 days after the last dose of study medication, study staff will call the patient to document any new events occurring within 28 days of the last dose (safety follow-up).

4.4 FOLLOW-UP FOR NEW SYSTEMIC TREATMENT, DISEASE RELAPSE, AND SURVIVAL

4.4.1 Long-term Follow-up

Once subjects discontinue glasdegib and start a new systemic immunosuppressive treatment, refuse to continue participation, or are diagnosed with relapsed malignancy, they will be followed via medical record review for new systemic cGVHD treatment, disease relapse, and survival.

4.5 MISSED EVALUATIONS

Missed evaluations should be rescheduled and performed as close to the original scheduled date as possible. An exception is made when rescheduling becomes, in the investigator's opinion, unsafe or medically unnecessary because it is too close in time to the next scheduled evaluation. In that case, the missed evaluation should be abandoned and the reason for the missed visit recorded in the database.

5.0 STATISTICAL METHODS OF ANALYSIS

5.1 GENERAL CONSIDERATIONS

This is a Phase I/II, single-arm trial designed to assess the safety and efficacy of glasdegib in subjects with sclerotic cGVHD.

5.2 RATIONALE FOR SAMPLE SIZE

With a sample size of 20 patients, the best ORR will be estimated with an 80% exact binomial confidence intervals (CIs).⁴³ If glasdegib is more effective than ibrutinib, the lower bound of the CIs will be used to provide evidence that the true ORR is greater than a specific response rate. For instance, if there are 17 response (CR+PR) out of 20 patients (85%), the corresponding 80% CI will exclude 67% which is greater than the published historical chronic GVHD trials with ORR 67%. However, even if glasdegib is not statistically more effective than ibrutinib, it may still be a preferable treatment if the toxicity is less or the response rate for sclerotic features is encouraging.

5.3 ANALYSIS POPULATIONS

All efficacy and safety analysis will be performed using the treated population, which consists of all subjects who receive any amount of study treatment. The characteristics of this population will be described. The analysis of duration of response will only include subjects who have achieved objective response.

5.4 MISSING DATA HANDLING

No imputation of values for missing data will be performed except: missing or partial start and end dates for AEs and concomitant medication will be imputed according to prespecified, conservative imputation rules. Subjects lost to follow-up (or drop out) will be included in statistical analyses to the point of their last evaluation.

5.5 ENDPOINT DATA ANALYSIS

5.5.1 Study Treatment Administration and Compliance

Descriptive information will be provided regarding the number of glasdegib cycles completed and the number and timing of prescribed dose delays, reductions and interruptions.

5.5.2 Analysis of Endpoints

5.5.2.1 Primary Endpoint

The primary endpoint is the safety and tolerability of glasdegib in the cGVHD population. This will be reported as the type and severity of adverse events, severe adverse events and number of cycles completed and reasons for discontinuation.

5.5.2.2 Secondary Endpoints

The secondary endpoints are best overall Response Rate (ORR) in sclerotic manifestations, best ORR in all cGVHD manifestations, and safety.

Overall Response Rate (ORR) in sclerotic manifestations

Best ORR of sclerotic manifestations by 12 months after the initiation of glasdegib and before another systemic immunosuppressive regimen is started represents the composite outcome of complete and partial response (CR + PR). ORR will be calculated according to (1) the response definitions of the NIH Consensus Conference for (a) skin or joint scores (0-3), where improvement by at least 1 point is a PR and return to score 0 is a CR, or (b) the photographic range of motion scale (0-25) where improvement by at least 1 point is a PR and return to score 25 is a CR; and (2) change in the 0-10 sclerotic severity scale where at least a 2 point improvement is a PR or return to 0 (CR).

Overall Response Rate (ORR) in all cGVHD manifestations

Best ORR of all cGVHD manifestations by 12 months after the initiation of glasdegib and before another systemic immunosuppressive regimen is started represents the composite outcome of complete and partial response (CR + PR). ORR will be calculated according to the response

definitions of the NIH Consensus Conference. ORR both including and excluding skin sclerotic features will be reported.

Safety

Safety assessments will consist of monitoring and recording adverse events. See section 6.0 below.

In addition, we will describe the following exploratory endpoints:

Failure-Free Survival

This endpoint will be estimated at 12 months with events considered death, relapse, or start of another systemic immunosuppressive agent. Patients lost to follow-up or who withdraw consent will be censored.

Patient-reported outcomes

Subjects will provide assessments of their symptom burden and quality of life using a validated instrument recommended by the NIH Consensus on Chronic GVHD (Lee Chronic GVHD Symptom Scale) and the NIH-endorsed PROMIS-29 (See Appendix 10). These will be collected before starting glasdegib on day 1 of cycle 1, and again on D1, cycles 4, 7, 10, 13, 16, 19, 22 and EOT. Scores will be calculated for each instrument based on published algorithms with absolute changes from baseline and clinically meaningful changes described for the population as a whole and based on CR+PR vs. SD+MR+PD.

Biologic studies

These studies aim to discern the biologic impact of Hedgehog pathway inhibition in the treatment of cGVHD and may include the following skin assays as well as others: expression of Shh, Gli1, Gli2, ptch-2, collagen, TGFb, and Smo. Immunohistochemistry may be performed for Patched, Shh, Snail, GSK3- β , β -catenin, or Ihh as well as other markers.

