1.0 BACKGROUND INFORMATION

1.1 CHRONIC GRAFT-VERSUS-HOST DISEASE

Chronic graft vs. host disease (cGVHD) is a major late complication of allogeneic hematopoietic cell transplantation (HCT) that affects up to 50% of HCT survivors. The syndrome is associated with major transplant-related morbidity, mortality, infectious complications, prolonged duration of immune suppression, and impaired patient-reported quality of life.¹⁻⁸ Thus, it represents a major obstacle to recovery and survival following HCT, and its prevention and treatment are of significant importance. Chronic GVHD is characterized by diverse clinical manifestations, but the most commonly affected organs are the skin, eyes, mouth, and liver.⁹ However, most organs can be involved, with parallels to other systemic immune-mediated disorders.

Sclerotic GVHD is a distinctive phenotype of cGVHD that usually begins in the superficial layers of the skin and then extends to deeper layers but it may also only involve deeper structures such as fascia with normal overlying skin. Sclerotic GVHD can severely affect patients' mobility and quality of life, and it is often refractory to standard and secondary therapies. The presence of sclerosis after allogeneic HCT is considered diagnostic for cGVHD.¹⁰ Progressive or poorly controlled sclerotic GVHD results in joint contractures, chronic skin ulcers, and pulmonary restriction, causing major disability. A prospective multicenter observational study found a cumulative incidence of 8% sclerosis with a median onset of 14 months.¹¹ In a large study from Fred Hutchinson Cancer Research Center, the cumulative incidence of sclerosis was 20% at 3 years. Of the patients who developed sclerosis, 13% had only skin sclerosis, 33% had only joint contracture or fasciitis, and 53% had both clinical manifestations. The development of sclerosis was associated with a reduced rate of withdrawal of immunosuppressive treatment.¹² These findings as well as clinical experience indicate that patients with sclerotic chronic GVHD have poor quality of life, often require multiple sequential therapies, and frequently exhaust available treatment options.¹³⁻¹⁵

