1.4 ASSESSMENT OF THERAPEUTIC RESPONSE IN CHRONIC GVHD

Following the 2014 NIH Consensus Conference, most clinical trials use the recommended response criteria to calculate response based on change scores in nine organ-specific measures, assessed prior to study treatment and at defined points afterwards. The organ-specific change scores are used to classify responses into complete (CR, resolution of all cGVHD manifestations), partial (PR, partial resolution of cGVHD manifestations without significant worsening in any organ), stable (SD, no change in organ involvement), mixed response (MR, improvement and worsening in different organs) and progressive (PD, significant worsening in at least one organ). The overall response rate (ORR) is the CR plus PR rate.²⁸

Interpretation of previously published trials for secondary cGVHD treatment is limited by a number of factors, most notably heterogeneity in response determination. In the Phase 2 ibrutinib study that led to regulatory approval (N=42), the best ORR was 67%. Adverse events were common including fatigue, diarrhea, muscle spasms, nausea and bruising.²⁷ The publication reported that at a median follow-up of 13.9 months, 30 (70%) had stopped treatment.

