Appendix 7. Response Determination

Response determination for chronic GVHD clinical trials based on clinician assessments

Organ	Complete Response	Partial Response	Progression
Skin	NIH Skin Score 0 after previous involvement	Decrease in NIH Skin Score by 1 or more points	Increase in NIH Skin Score by 1 or more points, except 0 to 1
Eyes	NIH Eye Score 0 after previous involvement	Decrease in NIH Eye Score by 1 or more points	Increase in NIH Eye Score by 1 or more points, except 0 to 1
Mouth	NIH Modified Oral Mucosa Rating Score 0 after previous involvement	Decrease in NIH Modified Oral Mucosa Rating Score of 2 or more points	Increase in NIH Modified Oral Mucosa Rating Score of 2 or more points
Esophagus	NIH Esophagus Score 0 after previous involvement	Decrease in NIH Esophagus Score by 1 or more points	Increase in NIH Esophagus Score by 1 or more points, except 0 to 1
Upper GI	NIH Upper GI Score 0 after previous involvement	Decrease in NIH Upper GI Score by 1 or more points	Increase in NIH Upper GI Score by 1 or more points, except 0 to 1
Lower GI	NIH Lower GI Score 0 after previous involvement	Decrease in NIH Lower GI Score by 1 or more points	Increase in NIH Lower GI Score by 1 or more points, except from 0 to 1
Liver	Normal ALT, alkaline phosphatase, and Total bilirubin after previous elevation of one or more	Decrease by 50%	Increase by 2x ULN
Lungs	-Normal %FEV1 after previous involvement -If PFTs not available, NIH Lung Symptom Score 0 after previous involvement	-Increase by 10% predicted absolute value of %FEV1 -If PFTs not available, decrease in NIH Lung Symptom Score by 1 or more points	-Decrease by 10% predicted absolute value of %FEV1 -If PFTs not available, increase in NIH Lung Symptom Score by 1 or more points, except 0 to 1
Joints and Fascia	Both NIH Joint and Fascia Score 0 and P-ROM score 25 after previous involvement by at least one measure	Decrease in NIH Joint and Fascia Score by 1 or more points or increase in P-ROM score by 1 point for any site	Increase in NIH Joint and Fascia Score by 1 or more points or decrease in P-ROM score by 1 point for any site
Global	Clinician overall severity score 0	Clinician overall severity score decreases by 2 or more points on a 0–10 scale	Clinician overall severity score increases by 2 or more points on a 0–10 scale

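### The sclerotic response rate sets no condition on worsening, so under component (1) skin that improves while joints progress (or the reverse) counts as a partial response

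*Combined protocol and SAP*

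**What the plan says.** Section 5.5.2.2 defines the sclerotic response rate as the best complete or partial response by 12 months, before any other systemic immunosuppressive regimen. It has two numbered components.

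- Component (1) takes the skin or joint score, each from 0 to 3, "where improvement by at least 1 point is a PR and return to score 0 is a CR, or (b) the photographic range of motion". The second option runs from 0 to 25, with a 1-point gain as partial response and 25 as complete response.
- Component (2), joined to (1) by the word and, is "change in the 0-10 sclerotic severity scale where at least a 2 point improvement is a PR or return to 0 (CR").

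Neither component says what happens if another sclerotic measure gets worse.

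Section 1.4 describes partial response as "partial resolution of cGVHD manifestations without significant worsening in any organ". It gives a separate category, mixed response, to improvement in one organ with worsening in another, and defines the overall response rate as complete plus partial response only. The patient-reported outcomes paragraph of Section 5.5.2.2 follows the same grouping: mixed response sits with stable and progressive disease, against complete and partial response.

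Appendix 7 treats Skin and Joints and Fascia as separate organs. Progression in Joints and Fascia is "Increase in NIH Joint and Fascia Score by 1 or more points or decrease in P-ROM score by 1 point for any site". The partial-response column of that row uses the same any-site wording for range-of-motion gains. Appendix 7 has no rule for combining organs and none for a row that meets two columns at once.

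**The concern.** Whether sclerosis improves is the first efficacy question listed in Section 2.2. Skin and joints/fascia are the two places where sclerosis is measured. A rule that credits improvement in one and ignores progression in the other can count as a responder someone whose sclerotic disease is advancing.

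Two features of the design make this more than a wording matter. The endpoint is the best response by 12 months, so one favourable visit is enough. And Section 3.10 lets patients continue glasdegib through chronic GVHD progression unless a new systemic agent is started, so patients with mixed change stay under assessment.

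**Working it through.** **1. One patient under each rule.** Take a skin score going from 3 to 2 and a joint/fascia score going from 1 to 3, both against baseline.

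- Section 5.5.2.2, component (1): the skin score improved by 1, so partial response. The joint score is not consulted.
- Appendix 7: the Skin row is partial response; the Joints and Fascia row is progression.
- Section 1.4: one organ better and another worse is mixed response, which is not in the overall response rate.

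The reverse patient (joint score 2 to 1, skin score 2 to 3) gives the same split.

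**2. Component (2).** The text allows two readings.

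- Separate calculations: the patient above is a responder under (1), with (2) reported alongside.
- Both required: the patient also needs a gain of at least 2 points on the 0-10 rating. Appendix 6 shows this as a single clinician rating of skin and/or joint tightening. It makes such a patient less likely to qualify, but it carries no condition on worsening in either tissue, so the gap narrows without closing.

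**3. Whether citing the NIH definitions closes the gap.** The citation reads "ORR will be calculated according to (1) the response definitions of the NIH Consensus Conference for (a) skin or joint scores (0-3"), so it attaches to named scores with thresholds written out. Appendix 7 supplies no combining rule to import. Section 5.5.2.2 also departs from Appendix 7 elsewhere: it accepts a joint score of 0 or a range-of-motion score of 25 alone as complete response, where Appendix 7 needs both. Unstated conditions therefore cannot be assumed to carry over.

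**4. Direction.** Responders as written = responders with no worsening + patients whose only qualifying visits are mixed. The last term cannot be negative, so the bias can only be upward. Appendix 2 schedules eight post-baseline assessments by 12 months (cycles 2 to 7, then 10 and 13: 6 + 2 = 8), any of which can supply the best response.

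**5. Size.** One patient of 20 is 1/20 = 5 percentage points. The documents give no rate of mixed change, so any total is an assumption.

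- Section 1.1 reports, for a cohort of patients who developed sclerosis, that "33% had only joint contracture or fasciitis, and 53% had both clinical manifestations". Applied to this trial: 0.53 × 20 = 10.6 patients with both.
- If 10% to 20% of them had mixed change (assumed, no source): 10.6 × 0.10 = 1.1 to 10.6 × 0.20 = 2.1 patients, or 5 to 11 points.
- This is close to an upper bound under that assumption, because a patient with one clean improved visit remains a responder.

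**6. What one patient can change.** Section 5.2 says 17 of 20 gives an 80% exact interval that excludes 67%. With Clopper-Pearson limits Beta(0.10; x, n − x + 1) and Beta(0.90; x + 1, n − x):

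- 17/20: 0.696 to 0.944, which excludes 0.67. The plan's statement is reproduced.
- 16/20: 0.639 to 0.910, which does not exclude 0.67.

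Section 5.2 does not say that its example concerns the sclerotic rate, so this shows only how sensitive 20 patients are to one reclassification.

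**7. The overlap in Appendix 7.** Shoulder +1 and ankle −1 meets the partial-response and progression columns of Joints and Fascia at the same visit. On the 0-25 total used in Section 5.5.2.2 the change is +1 − 1 = 0, so this patient gains no sclerotic response from range of motion. The ambiguity falls on the all-manifestations rate, which follows the NIH organ definitions.

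**The case against.** The strongest reply is that Section 1.4 is background. It describes overall response across nine organ measures and does not set a rule for a sclerosis-only endpoint. The next endpoint in Section 5.5.2.2, response in all manifestations, can still class these patients as mixed. That is fair as to status. But Section 1.4 holds the plan's only definition of mixed response and its only cross-organ definition of partial response, and the analysis section itself treats mixed response as non-response. A sclerotic endpoint meant to work differently should say so.

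A second reply is that component (2) may be mandatory. That stands as a limit. A reader might infer that every patient with skin better and joints worse is a sclerotic responder on a 1-point change; the text supports that only if (1) and (2) are separate.

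Three other strong readings are not supported:

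- That equal and opposite range-of-motion changes at different sites create sclerotic responders. They cancel on the total score.
- That one or two extra responders should be expected. The mixed rate has no source, and the 53% comes from a cohort, not from this trial's eligible patients.
- That the error rate of the two-stage futility rule in Section 3.12 is inflated. That rule refers to overall response rate without saying which one, and no test or decision is tied specifically to the sclerotic rate.

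**Conclusion.** The omission is real, and it conflicts with the plan's own use of partial and mixed response. Under component (1), improvement in one sclerotic organ counts whatever happens in the other. Whether that alone makes a sclerotic responder depends on how the two components combine, which the plan leaves open; under either reading nothing rules out worsening.

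The bias is upward only. Its size is unknown, at 5 percentage points per reclassified patient. The endpoint is secondary, since the primary is safety and tolerability, so this does not threaten the trial's main conclusion. It does affect how the first-listed efficacy result can be read. The Appendix 7 overlap is a separate, smaller gap that bears on the all-manifestations rate.

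**What to change.** - **Section 5.5.2.2.** State that a sclerotic partial or complete response at a visit requires the existing improvement criteria and, at that visit, no worsening from baseline of 1 or more points in the skin score, the joint/fascia score or the total range-of-motion score. Otherwise the visit is mixed and is not a response. Keep component (2), and say whether it is required jointly with (1) or calculated separately. Using the total range-of-motion score stops a change at one site from overriding the total-score rule already in the section. Say also whether the exception in Appendix 7 for a skin score going from 0 to 1 applies here.
- **Sensitivity analysis.** Report the sclerotic rate without the no-worsening condition alongside.
- **Appendix 7.** When Joints and Fascia meets both columns at a visit, it does not count as a partial response for overall response.

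The cost is a few sentences. The response form in Appendix 6 already records skin, joint/fascia, range of motion and the 0-10 rating together, so no new visits or data are needed. The downside is that the reported response rates may be slightly lower.
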